#### **4.4 Withdrawal of Subjects**

Subjects can voluntarily withdraw (or be withdrawn) at any time during the study.

Investigators may withdraw a subject from the study because:

- A new health condition, diagnosis or finding appears that is suspected to require care or medication prohibited by the protocol.
  - e.g., the planned surgical procedure is modified to a procedure prohibited by the protocol.
- The subject has unacceptable adverse events.
- It is in the subject's best interest according to the Investigator's clinical judgment.

If a subject is prematurely withdrawn from the study, the reason(s) for withdrawal must be recorded on the subject's Subject Completion case report form (CRF).

Subjects who discontinue the study prematurely will not be replaced.

## **5 RANDOMIZATION, BLINDING AND SUBJECT IDENTIFICATION PROCEDURES**

### **5.1 Randomization**

Patients will be prospectively randomized into the PILLAR III Clinical Trial. Randomization will occur at the time of surgery, just after induction of anesthesia. Prior to surgery the patient will have provided written informed consent, completed all baseline procedures and met the requirements of the study inclusion and exclusion criteria. Randomization should be performed as closely as possible to the point of resection to minimize the incidence of dropout.

Patients will be randomly assigned on a one to one (1:1) basis to either the PERFUSION group (PFN) or the STANDARD group (STD). Randomization will be stratified by study site and within site by the patients history of prior neoadjuvant therapy (chemotherapy and/or radiation vs. non-neoadjuvant therapy) to ensure a more even distribution of baseline neoadjuvant therapy between treatment groups. Permuted block randomization will be performed within strata. To minimize the opportunity for the sequence to be predicted, the block size will be variable and randomly chosen from small multiples of 2 (i.e. 2, 4 or 6). The randomization schedules for all strata will be generated in advance by the contracted study statistician or designee using a computerized

random number generator. Investigational sites and the Study Sponsor will not have access to the randomization schedules.

Randomization will be accomplished using a sequential numbered sealed envelope system. Due to stratification for prior neoadjuvant therapy, a box of envelopes will be supplied for each strata (one for subjects who have received prior neoadjuvant therapy and another for subjects who have not received prior neoadjuvant therapy). Envelope seals are broken and treatment assignment is made only after verification of proper informed consent execution and study eligibility. In order to prevent any attempts to subvert the randomization process, the subject's initials, date of birth and date of randomization will be written on the randomization card. The randomization card will be signed by the study coordinator performing the randomization procedure and a second researcher who will witness the randomization procedure.

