## 1.2 Previous Human Experience

Several studies using similar technology to PINPOINT and SPY Elite have been conducted to investigate the feasibility of using NIR ICG induced fluorescence angiography in assessing tissue perfusion during colorectal resection to potentially reduce the rate of anastomotic leak have been published.

The PILLAR II study was conducted to demonstrate the utility and feasibility of intra-operative perfusion assessment using PINPOINT NIR ICG induced fluorescence angiography at the time of anastomosis creation.

One hundred and forty-seven patients were enrolled, of whom 139 were eligible for final analysis. The average age of patients was 58  $\pm$ 14 years, and 53% of patients were male. Obesity (Body Mass Index [BMI]  $>30$ ) was prevalent in 30% and the majority of patients were American Society of Anesthesiologists (ASA) II (53%). Diverticulitis (44%), rectal cancer (25%) and colon cancer (21%) were the most prevalent pre-operative diagnoses. Of the patients with rectal cancer (N=35), 43% underwent pre-operative pelvic radiation. Cardiovascular disease (44%), and urogenital disease (40%) were the most prevalent comorbidities.

Laparoscopic resection was attempted in 86% and robotic surgery in 14% of the patients imaged. There was an overall conversion rate of 7.8% (N=12), of which 5 patients were imaged, and 7 patients were dropped out of analysis due to intraoperative decision to not image. The splenic flexure was mobilized in 81% of patients, and a high ligation of the inferior mesenteric artery (IMA) was performed in 62% of cases. Successful imaging was obtained in 98.6% of cases in which perfusion imaging was attempted. Imaging was unsuccessful in 2 patients secondary to equipment malfunction. Fluorescence angiography imaging changed the surgical plan in 11 (7.9%) patients. This included revision of the point of proximal colon transection as indicated by perfusion assessment in 9 patients (6.5%); takedown and revision of anastomosis after transanal perfusion assessment in one patient; and confirmation of viability of anastomosis where there was concern based on white light imaging in one patient. The use of fluorescence angiography with findings of adequate perfusion altered the intraoperative plan for diversion to no diversion in this patient. There were no anastomotic leaks in the 11 patients in whom a change in the surgical plan occurred based on fluorescence angiography findings.

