#### 5.1.1 Randomization Procedure

The study coordinator or a designee will log into the EDC system and be asked a series of questions verifying that the patient is eligible and that informed consent has been obtained prior to initiating the randomization process. Once the subject is under anaesthesia, the study coordinator will select the randomization envelope with the lowest randomization number from the neoadjuvant or non-neoadjuvant randomization box depending on if the subject has received prior neoadjuvant therapy or not. The study coordinator will then disclose the randomization assignment to the Investigator. The study coordinator will then write the subject's initials, date of birth, and date of randomization on the randomization card. A second study coordinator or designee will witness the randomization procedure and will sign and date the randomization card verifying that the randomization procedure was followed correctly. The randomization card will be maintained in the subject's file. As there is no ability for a sham comparison, the investigator cannot be blinded to the use of the PINPOINT or SPY Elite device. Patients will be blinded to their randomization assignment until after the procedure.

A subject is not randomized until a randomization envelope seal has been broken. The randomization procedure should not be initiated unless the EDC system confirms that a patient is eligible and verifies baseline information. If any deviations occur (errors such as misplacing envelopes), or if the randomization assignment is made incorrectly, the clinical site will be required to contact the Sponsor and await guidance on how to proceed.

If, at any time after randomization, the subject becomes ineligible or withdraws, the subject is still considered randomized. If an intraoperative decision is made to perform a procedure other than what was intended, the subject will be categorized with respect to the definitions outlined for the analysis populations (see the Statistical Methods Section 10.6).

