#### 8.3.2.2 Proximal Transection Margin

At the point of the procedure when the colon/rectum has been mobilized and dissected fully and appropriately, the distal rectal transection has been completed, the IMA and IMV have been ligated, and the surgeon is prepared for proximal resection and subsequent low anastomosis, perfusion assessment will be performed.

Perfusion assessment of the proximal transection margin may be made with PINPOINT or SPY Elite depending on Investigator preference and approach (open vs minimally invasive).

The location of proximal transection will be based on clinical judgment and will include consideration of the following factors:

- A minimum distance of 5 cm from the tumor for the proximal resection margin.
- Sufficient bowel length to ensure a tension-free anastomosis.
- Preservation of bowel length.
- Adequate blood supply through visual inspection and palpation using the following assessment techniques where appropriate:
  - pink tissue with 1-2 second refill.
  - bleeding (bright red) from the cut edge or from abrasion or stabbing with needle.
  - presence of blood in bowel vasculature.

ICG will be administered and the surgeon will assess perfusion of the tissue around (proximal and distal to) the planned transection margin.

Perfusion imaging of the proximal transection margin may be performed intracorporeally or extracorporeally depending on Investigator preference. If proximal imaging is performed extracorporeally, all fluorescent lights must be turned off to minimize background noise.

The PINPOINT imaging head will be positioned between 5 cm and 30 cm (~2-12 inches) from the planned transection margin with the camera head positioned parallel to the area being imaged and planned transection margin centered in the field of view. The area being imaged must remain in focus throughout the imaging procedure.

If the Investigator chooses to utilize SPY Elite for proximal imaging, the following procedure will be followed. The SPY Elite Imaging head will be positioned parallel to the proximal colon, approximately 30 cm (~12 inches) from the bowel, with the proximal transection margin centered

in the field of view. SPY Elite imaging may be performed for proximal transection margin imaging in open procedures or for extracorporeal minimally invasive procedures.

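### Protocol 5.1 and SAP 3.4 give two randomisation times that do not agree; a site using the earlier one tells the surgeon the arm before mobilisation, vessel ligation and distal transection, with no benefit.

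*Protocol*

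**What the plan says.** Protocol 5.1 contains two timing statements in one paragraph. The first is a firm rule: "Randomization will occur at the time of surgery, just after induction of anesthesia". The second is guidance: "Randomization should be performed as closely as possible to the point of resection to minimize the incidence of dropout". SAP 3.4 repeats both.

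Section 5.1.1 gives the working procedure: "Once the subject is under anaesthesia, the study coordinator will select the randomization envelope with the lowest randomization number", taken from the box for the subject's neoadjuvant stratum. Then: "The study coordinator will then disclose the randomization assignment to the Investigator". The same section accepts that "the investigator cannot be blinded to the use of the PINPOINT or SPY Elite device", because no sham comparison is possible. A subject who later becomes ineligible or withdraws remains randomised.

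The other timing references are looser. The Protocol Summary, 3.1 and 8.3 say only that randomisation takes place during anaesthesia. Table 1 puts it in the operating room during anaesthesia, in the intra-operative column. In 8.3, one Operative CRF item treats the start of the operation and the time of randomisation as a single time point.

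Section 8.3.2.2 sets these conditions for the first perfusion assessment: "the colon/rectum has been mobilized and dissected fully and appropriately, the distal rectal transection has been completed, the IMA and IMV have been ligated". Readiness for proximal resection is the last condition listed there.

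**The concern.** The two arms are meant to share the same operation up to the first imaging step. Lack of blinding is unavoidable from that step on, but the reason given for it (no sham is possible) does not apply earlier. Under the early timing the surgeon performs all the shared surgery knowing the arm.

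Two things are at stake.

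- **Performance bias.** Level of vessel ligation, conversion and final anastomosis height are decided or shaped before imaging. Section 1.1 names tension and tissue ischemia among the technical causes of anastomotic complications and says leak risk rises for lower anastomoses. A difference between arms in these steps could affect leak rates without any contribution from imaging.
- **Exclusions made with the arm known.** Protocol 10.5.1 and SAP 4.2.3 remove aborted resections from the mITT population, and 4.4 allows withdrawal, without replacement, when the procedure changes to a prohibited one. Under the early timing, the person making those decisions knows the assignment. Subjects whose operation changes before imaging are already randomised, so they either leave the analysis or dilute it.

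**Working it through.** **Step 1. Sequence of events under each timing.**

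| Event | Early timing (just after induction) | Late timing (close to resection) |
|---|---|---|
| Envelope opened, arm disclosed | before surgery starts | after most of the dissection |
| Exploration, mobilisation, IMA/IMV ligation, distal transection | arm known | arm largely unknown, depending on the moment chosen |
| Decision to abort or change the procedure before imaging | arm known, subject randomised | mostly arm unknown, subject not yet randomised |
| First imaging, proximal transection, anastomosis, diversion | arm known | arm known |

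The second statement in 5.1 names no operative step, so sites can follow either column and still claim to comply. Section 5.1 lists the subject's initials, date of birth and date of randomisation for the randomisation card. It does not list clock time, so the card as described would not show which timing a site used.

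**Step 2. Reproduce the plan's power figure.** Inputs are from Protocol 10.4 and the rationale text run into the 10.5 heading: leak rates 12.5% and 6.25%, one-sided alpha 0.025, looks at 450 and 800 with Pocock-type alpha spending, and a pooled z-test. Allocation is 1:1, so 225 and then 400 per arm.

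- Information fraction t = 450/800 = 0.5625.
- Interim alpha = 0.025 × ln(1 + (e − 1) × 0.5625) = 0.0169, as stated. Bound z₁ = 2.122.
- Final bound, solved from the bivariate normal with correlation √0.5625 = 0.75: z₂ = 2.220.
- Null variance term: mean rate 0.09375, so 2 × 0.09375 × 0.90625 = 0.16992. Alternative variance term: 0.125 × 0.875 + 0.0625 × 0.9375 = 0.16797.
- Drift = 0.0625 × √(n / 0.16797) = 2.287 at n = 225 and 3.050 at n = 400.
- Bounds rescaled by √(0.16992/0.16797) = 1.0058: 2.135 and 2.233.
- Power = 1 − P(Z₁ < 2.135 − 2.287, Z₂ < 2.233 − 3.050) = **81.7%**, against 81.6% stated.

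**Step 3. Illustrate the effect of subjects who cannot be imaged.** The documents give no such rate for this trial. For scale only, section 1.2 reports that in PILLAR II "7 patients were dropped out of analysis due to intraoperative decision to not image": 7/147 = 4.8% of those enrolled. The 10% row is an assumption with no source. Let u be the share, applied in one of three ways:

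- (a) Kept in mITT at the control leak rate: PERFUSION rate = 0.0625 + 0.0625u.
- (b) Excluded from both arms: n multiplied by (1 − u).
- (c) Kept in both arms but unable to leak (no anastomosis): both rates multiplied by (1 − u).

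| u | (a) kept, control rate | (b) excluded | (c) cannot leak |
|---|---|---|---|
| 4.8% | 77.1% | 79.8% | 79.5% |
| 10% | 71.5% | 77.4% | 76.9% |

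For example, (a) at 4.8% uses a PERFUSION rate of 0.0625 + 0.0476 × 0.0625 = 6.55%. At 10%, (b) has 720 subjects and (c) has rates of 11.25% and 5.625%.

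**Step 4. Performance bias.** The documents give nothing from which to estimate it. As a sensitivity figure only: if imaging had no effect but knowledge of the arm lowered the PERFUSION leak rate by 1 or 2 points from 12.5%, the same design would declare success with probability 5.8% or 12.4% rather than 2.5%.

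**The case against.** The strongest reply is that the plan already intends a late draw. The second sentence in 5.1 states that aim and gives the dropout reason for it. Being under anaesthesia (5.1.1) can be read as the earliest permitted time, not the latest. Most other references, including Table 1, say only during anaesthesia. This stands in part: a reader might infer that Table 1 fixes the early timing, and it does not. But the induction sentence is a flat statement set against a recommendation that names no surgical step, and the 8.3 CRF item ties randomisation to the start of the operation.

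Second, the shared surgery is less free than it might seem. Section 3.1 requires early devascularization and splenic flexure mobilisation in both arms. Planned anastomosis height is settled at eligibility (4.2), so only final height can move. Section 8.3.1 applies the ASCRS guidelines and asks for deviations to be recorded. Ligation level, conversion and final height go on the Operative CRF, so an imbalance would be visible. All of this stands. It limits the room for bias but does not remove it.

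Third, a reader might take the 6-24% conversion range in section 1.1 as the share who would go un-imaged. The documents do not support that: open surgery is allowed, SPY Elite may be used in open procedures (8.3.2.2), and 5 of the 12 converted PILLAR II patients were imaged. The 7/147 figure is itself only a rough marker. That study attempted laparoscopic or robotic resection only, and its stated 7.8% for 12 conversions implies a denominator near 154, since 12/147 is 8.2%.

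Fourth, column (a) does not fit everyone affected. Aborted resections leave mITT, and a subject without an anastomosis cannot leak. Columns (b) and (c) show a markedly smaller loss. This stands, which is why a range is given.

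**Conclusion.** The text conflict is certain and appears in both documents. Under the early timing, the surgeon knows the arm through mobilisation, ligation and distal transection and when deciding whether to abort or change the procedure, although nothing in the trial needs the arm to be known then. Correcting this is a worthwhile, inexpensive improvement that serves the plan's own stated aim.

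The size is not established. Against the protocol's N = 800 design, an assumed 4.8% of subjects who cannot be imaged gives power of about 77% (kept at the control rate) to 80% (excluded or unable to leak). An assumed 10% gives about 71.5% to 77%. These are illustrations: the shares are assumptions, and SAP 3.3 replaces that sample size with all subjects enrolled through March 31, 2017, with no formal calculation.

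A reader might infer that the primary comparison is biased, or that a power loss of this order should be expected. The documents support neither. They show that the opportunity exists, not how often it would be taken, and they leave open how many sites would randomise early.

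**What to change.** - In Protocol 5.1, 5.1.1 and 8.3, and in SAP 3.4, delete the phrase placing randomisation just after induction. Have the envelope opened at the decision point of 8.3.2.2, where "the distal rectal transection has been completed, the IMA and IMV have been ligated, and the surgeon is prepared for proximal resection": that is, with an eligible anastomosis still intended and before the proximal margin is assessed.
- Align the 8.3 Operative CRF item that equates the start of the operation with randomisation, and state the milestone in Table 1.
- Optional: before the envelope is opened, record the planned proximal transection point and whether diversion is intended, in both arms. Section 8.3 already captures the criteria for both decisions, so this is an addition rather than a repair.

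Cost: a protocol amendment and matching SAP text, with no additional patients. The coordinator and witness must be available mid-operation, and the imaging system must be ready in every case. Subjects found unsuitable before the milestone become screen failures. Decisions after that point (proximal transection, revision, diversion, leak classification) remain unblinded.

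If enrolment has already closed under SAP 3.3, timing can no longer be changed. The remaining step is to report when envelopes were opened, where recorded, and to tabulate ligation level, conversion, final height, aborted resections and withdrawals by randomised arm.

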#### 5.1.1 Randomization Procedure

The study coordinator or a designee will log into the EDC system and be asked a series of questions verifying that the patient is eligible and that informed consent has been obtained prior to initiating the randomization process. Once the subject is under anaesthesia, the study coordinator will select the randomization envelope with the lowest randomization number from the neoadjuvant or non-neoadjuvant randomization box depending on if the subject has received prior neoadjuvant therapy or not. The study coordinator will then disclose the randomization assignment to the Investigator. The study coordinator will then write the subject's initials, date of birth, and date of randomization on the randomization card. A second study coordinator or designee will witness the randomization procedure and will sign and date the randomization card verifying that the randomization procedure was followed correctly. The randomization card will be maintained in the subject's file. As there is no ability for a sham comparison, the investigator cannot be blinded to the use of the PINPOINT or SPY Elite device. Patients will be blinded to their randomization assignment until after the procedure.

A subject is not randomized until a randomization envelope seal has been broken. The randomization procedure should not be initiated unless the EDC system confirms that a patient is eligible and verifies baseline information. If any deviations occur (errors such as misplacing envelopes), or if the randomization assignment is made incorrectly, the clinical site will be required to contact the Sponsor and await guidance on how to proceed.

If, at any time after randomization, the subject becomes ineligible or withdraws, the subject is still considered randomized. If an intraoperative decision is made to perform a procedure other than what was intended, the subject will be categorized with respect to the definitions outlined for the analysis populations (see the Statistical Methods Section 10.6).

## 5.2 Subject Identification

Screening ID Number: All subjects screened for the study shall be assigned a 5-digit "screening" number on the Screening Log and if they are randomized, will subsequently be assigned a Subject Identification Number in the electronic data capture system. The Screening Identification Number shall be unique and categorize a subject in sequence of screening by an "S" followed by a 5-digit number. The first 2 digits identify the site and the last three digits identify the subject. For example, the first subject screened at site 01 is identified as screening number S-01-001. The screening log shall be maintained by the site to identify those subjects that have failed screening with the

reason why they did not qualify for enrollment. The screening number will be assigned sequentially within each study center in order of subject presentation for screening.

**Enrolled Subject ID Number:** Once a subject is randomized, they will be assigned a Subject Identification Number which is also a 5-digit number. The first two digits of the Subject Identification Number identify the site and the last three digits identify the subject. Each site will be given a Site Identification Number. For example, the first subject randomized at site 01 is identified as subject 01-001, the next subject as 01-002, etc.

## 6 STUDY TREATMENTS

### 6.1 PINPOINT Endoscopic Device Specifications

PINPOINT is an endoscopic fluorescence imaging system for high definition (HD) visible (VIS) light and near-infrared (NIR) fluorescence imaging. PINPOINT includes the following components:

- A surgical endoscope optimized for VIS/NIR illumination and imaging, which is available in different diameters, lengths and directions of view (Model: SC9100, SC9130).
- A camera head that is also optimized for VIS/NIR imaging and mounts to the endoscope eyepiece (Model: PC9002).
- A flexible light guide cable (Model: PC9004).
- An endoscopic Video Processor / Illuminator (VPI) capable of providing VIS/NIR illumination to the surgical endoscope via a flexible light guide cable, and the image processing required to generate simultaneous, real-time HD video color and NIR fluorescence images (Model: PC9001).

PINPOINT is designed to be connected to a medical-grade HD color monitor, such as those normally used in surgical endoscopy.

- PINPOINT Procedure Kits with Introducer containing the imaging agent, aqueous solvent and disposable rigid scope introducer (DRSI).

PINPOINT is connected to a high-definition medical video recorder (Sony HVO-1000) that allows the capture of still images and video during operation.

PINPOINT acquires NIR fluorescence images of an imaging agent (ICG) to allow for visual assessment of vessels, blood flow and related tissue perfusion during minimally invasive, or open surgery. For the purpose of this study, PINPOINT will be used to assess perfusion of colon and rectal tissue during low anterior resection procedures.

PINPOINT Procedure Kits are supplied as part of the PINPOINT System. The PINPOINT PAQ® contains 6 procedure kits and is indicated for use exclusively with PINPOINT.

Each PINPOINT PAQ® (Product code: PP9036) contains:

- One box of sterile indocyanine green for injection, USP that contains:
  - Six single use 25 mg vials of ICG
  - Six single use 10 ml ampules of sterile Aqueous solvent

- Twelve 3 ml syringes, sterile
- Twelve 10 ml syringes, sterile
- Six 3-way stopcocks, sterile
- Twelve needles, 18G, 1 inch, sterile
- Labels for syringes

The PINPOINT Operator's Manual describes the contents, use and storage of the PINPOINT PAQ's. Instructions for preparation, handling and administration of ICG are also provided in the PINPOINT Operator's Manual.

PINPOINT allows simultaneous display of multiple images. Real time NIR fluorescence video images are acquired by using the imaging agent and may be viewed in two ways:

PINPOINT image: NIR fluorescence is superimposed in pseudo-color (green) on a white light image

SPY image: A black and white NIR fluorescence image is displayed

PINPOINT also operates as a conventional endoscopic imaging system and provides illumination for real-time color (white light) HD video imaging in the area of interest.

PINPOINT is a commercially available product in the United States (US). PINPOINT has a 510(k) clearance from the FDA for the following indication:

***“The PINPOINT system is intended to provide real-time endoscopic visible and endoscopic NIR fluorescence imaging. PINPOINT enables surgeons to perform routine visible light endoscopic procedures as well as further visually assess vessels, blood flow and related tissue perfusion with near infrared imaging during minimally invasive surgery”.***

PINPOINT is manufactured by Novadaq Technologies Inc. (Novadaq). Please refer to the current version of the PINPOINT Operator's Manual for a full description and specifications of the system.

